3.2.1.4. Progression-free Survival

Progression-free survival (PFS) is defined as the time from the 'start date' until PD per Lugano Response Classification Criteria 2014, or death due to any cause, whichever occurs first.

3.2.2. Safety Endpoints

3.2.2.1. Adverse Events

Adverse Events (AEs) as graded by the NCI CTCAE v5.0 and coded using MedDRA.

3.2.2.2. Laboratory Parameters

Laboratory abnormalities as graded by the NCI CTCAE v5.0. For laboratory tests without NCI CTCAE grade definitions, results will be categorized as normal, abnormal, or not done.

3.2.3. Pharmacokinetic Endpoints

- Pre- and post-dose concentrations of PF-07901801.
- Pre-dose concentrations of Tafasitamab.
- Pre-dose concentrations of Lenalidomide.

3.2.4. Immunogenicity Endpoints

Incidence and titers of ADAs and NAbS against PF-07901801 and tafasitamab.

3.3. Exploratory Endpoints

CCI

3.4. Baseline Variables

In this study, 'study drug' refers to PF-07901801 or tafasitamab or lenalidomide, and 'study treatment' refers to PF-07901801 plus tafasitamab plus lenalidomide.

Start and end dates of study treatment:

The date of first dose of study treatment is the earliest date of the first non-zero dose date for the study drugs in the combination.

The date of last dose of study treatment is the latest date of the last non-zero dose date for the study drugs in the combination.

Definition of baseline:

Definition of baseline for efficacy analyses

The last measurement prior to or on the 'start date' will serve as the baseline measurement for efficacy analyses. For Phase 2 patients, if such a value is missing, the last measurement prior to the first dose of study treatment will be used as the baseline measurement except for analyses of tumor data where the baseline assessment would be considered as missing.

Definition of baseline for safety analyses

The last available assessment prior to the start of study treatment is defined as 'baseline' value or 'baseline' assessment for safety analyses. If an assessment is planned to be performed prior to the first dose of study treatment in the protocol and the assessment is performed on the same day as the first dose of study treatment, it will be assumed that it was performed prior to study treatment administration, if assessment time point is not collected or is missing. If assessment time points are collected, the observed time point will be used to determine pre-dose on study day 1 for baseline calculation. Unscheduled assessments will be used in the determination of baseline. However, if time is missing, an unscheduled assessment on study day 1 will be considered to have been obtained after study treatment administration.

Patients who start treatment and discontinue from the treatment/study on the same day may have two different sets of data collected on study day 1 (one during study and one in the End of Treatment (EOT) visit. Data reported at the EOT visit are not eligible for baseline selection.

If a scheduled pre-dose measurement actually occurred post-dose, then the corresponding measurement will be treated and analyzed similar to an unscheduled post-dose measurement.

3.5. Safety Endpoints

3.5.1. Adverse Events

Treatment-Emergent Adverse Events

Treatment-emergent adverse events (TEAEs) are those events with onset dates occurring during the on-treatment period, or if the worsening of an event is during the on-treatment period.

On-treatment period is defined as the time from the first dose of study treatment through minimum (28 days + last dose of study treatment, start day of new anti-cancer drug therapy – 1 day). The start day of new anti-cancer drug therapy after the first dose of study treatment is derived as outlined in Section [5.2.5](#).

4. ANALYSIS SETS (POPULATIONS FOR ANALYSIS)

For purposes of analysis, the following analysis sets are defined.

Population	Description	Applicable Analysis (for additional information refer to section 6)
DLT Evaluable Set	
All enrolled participants who receive at least 1 dose of the study treatment in the Phase 1b of the study and either experience DLT(s) or complete the DLT observation period without DLT. Participants without DLTs who receive less than 80% of the planned dose of PF-07901801 or less than 75% of the planned dose of any component of the tafasitamab and lenalidomide regimen in the DLT observation period are not evaluable for DLTs.
 
The DLT observation period is 28 days following C1D1.
	Primary endpoint, main analysis (section 6.1.1.1)
Safety Analysis Set	All enrolled participants who received at least 1 dose of study treatment.	
Primary endpoint, main analysis (Section 6.1.2.1)
 
Secondary endpoints (Section 6.2)

PK Analysis Set	The PK analysis set will include all participants in the safety analysis set who have at least 1 post-dose concentration measurement.	Secondary endpoints (Section 6.3.1)
Immunogenicity Analysis Set	All participants in the safety analysis set who have at least 1 sample tested for ADA.	Secondary endpoints (Section 6.3.2)
Biomarker Analysis Set	
All participants in the safety analysis set who have at least 1 baseline biomarker assessment.
 
Analysis sets will be defined separately for biomarkers based on CCI
	Exploratory endpoints (Section 6.4.1)

“Enrolled” means a participant’s, or their legally authorized representative’s, agreement to participate in a clinical study following completion of the informed consent process and assignment to study treatment.

5. GENERAL METHODOLOGY AND CONVENTIONS

5.1. Hypotheses and Decision Rules

5.1.1. Hypotheses and sample size determination

Phase 1b

For Phase 1b of this combination, due to the dynamic nature of the Bayesian allocation procedure, the exact sample size of the “Up-and-Down” matrix design using the mTPI-2 approach cannot be determined in advance. It is expected that up to 20 patients will need to be enrolled in Phase 1b using the mTPI-2 approach.

Phase 2

Up to 2 fixed doses will be selected for further evaluation in Phase 2 of the study. Approximately 25 participants will be treated for each selected dose. With 25 participants per arm, ORR can be estimated with a maximum standard error of 10%. Table 2 provides the 95% CIs for ORR based on Wilson method (with continuity correction) for different observed responses.

Table 2 Sample Size and 95% CI for ORR based on Wilson Method (with Continuity Correction)

N=25	Number of responses	Observed ORR	95% CI for ORR
	1	0.04	0.002, 0.223
	2	0.08	0.014, 0.275
	3	0.12	0.032, 0.323
	4	0.16	0.053, 0.369
	5	0.2	0.076, 0.413
	6	0.24	0.102, 0.455
	7	0.28	0.129, 0.496
	8	0.32	0.157, 0.536
	9	0.36	0.187, 0.574
	10	0.4	0.218, 0.611
	11	0.44	0.250, 0.647
	12	0.48	0.283, 0.682
	13	0.52	0.318, 0.717
	14	0.56	0.353, 0.750
	15	0.6	0.389, 0.782
	16	0.64	0.426, 0.813
	18	0.72	0.504, 0.871
	20	0.8	0.587, 0.924
	22	0.88	0.677, 0.968

5.1.2. Decision Rules

Phase 1b

The mTPI-2 design (with target pT=0.3, e1=0.05, e2=0.05) will be utilized to estimate the MTD of PF-07901801, in combination with standard doses of tafasitamab and lenalidomide. Other evidence such as safety data beyond DLT window, clinical activity, PK, PD and biomarker data will also be evaluated in determining the recommended doses for further development in the Phase 2.

The mTPI-2 design uses a Bayesian statistics framework and a beta binomial hierarchical model to compute the unit probability mass (UPM; the ratio of the probability mass of the interval to the length of the interval) of dosing intervals. The dose interval that has the largest UPM is selected as the winning model. The dose de-escalation/escalation recommendation for the mTPI-2 design with target $pT=0.3$, $e1=0.05$, $e2=0.05$ is as follows:

- If intervals $\{(0.15, 0.25), (0.05, 0.15), (0, 0.05)\}$ exhibit the largest UPM: escalate to next higher dose;
- If interval $(0.25, 0.35)$ exhibits the largest UPM: stay at current dose;
- If intervals $\{(0.35, 0.45), (0.45, 0.55), (0.55, 0.65), (0.65, 0.75), (0.75, 0.85), (0.85, 0.95), (0.95, 1)\}$ exhibit the largest UPM: de-escalate to next lower dose.

The detailed decision rules for mTPI-2 design with target $pT=0.3$, $e1=0.05$, $e2=0.05$ are listed in [Table 3](#).

Table 3 mTPI-2 Decision Rules (pT=0.3, e1=0.05, e2=0.05)

Number of Patients with DLTs	Number of Patients														
	1	2	3	4	5	6	7	8	9	10	11	12	13	14	15
0	E	E	E	E	E	E	E	E	E	E	E	E	E	E	E
1	D	D	S	S	E	E	E	E	E	E	E	E	E	E	E
2		DU	D	D	D	S	S	S	E	E	E	E	E	E	E
3			DU	DU	D	D	D	D	S	S	S	S	E	E	E
4				DU	DU	DU	D	D	D	D	D	S	S	S	S
5					DU	DU	DU	DU	DU	D	D	D	D	D	S
6						DU	DU	DU	DU	DU	DU	D	D	D	D
7							DU	D	D						
8								DU							
9									DU						
10										DU	DU	DU	DU	DU	DU
11											DU	DU	DU	DU	DU
12												DU	DU	DU	DU
13													DU	DU	DU
14														DU	DU
15															DU

E = Escalate to the next higher dose level

S = Stay at the current dose level

D = De-escalate to the next lower dose level

DU = The current dose level is unacceptably toxic and should be eliminated from further dose finding

Phase 2

There are no formal decision rules for Phase 2.

5.2. General Methods

Unless otherwise specified, all efficacy analyses and safety analyses will be performed using the Safety Analysis Set. All analyses will be performed by phase and by treatment group (i.e. dose level) as follows:

- Phase 1b
 - Dose level 1
 - Dose level 2
 - Dose level 3

- Phase 2
 - Selected fixed dose level 1
 - Selected fixed dose level 2

5.2.1. Data Handling After the Cutoff Date

Data after the cutoff date may not undergo the cleaning process and will not be displayed in any listings or used for summary statistics, statistical analyses or imputations.

5.2.2. Pooling of Centers

In order to provide overall estimates of treatment effects, data will be pooled across centers. The 'center' factor will not be considered in statistical models or for subgroup analyses due to the high number of participating centers in contrast to the anticipated small number of participants enrolled at each center.

5.2.3. Analyses to Assess the Impact of COVID-19 Pandemic

Data summaries and analyses may be performed to assess the impact of COVID-19 on the trial population and study data. Details of these summaries and analyses are included in the respective sections.

5.2.4. Definition of Study Day

Start day of study treatment is the day of the first dose of study treatment.

The study day for assessments occurring on or after the start of study treatment (e.g., adverse event onset, disease measurement) will be calculated as:

Study day = Date of the assessment/event – start of study treatment + 1.

The study day for assessments occurring prior to the first dose of study treatment (e.g., baseline characteristics, medical history) will be negative and calculated as:

Study day = Date of the assessment/event – start of study treatment.

The study day will be displayed in all relevant data listings.

5.2.5. Definition of start of new anti-cancer drug therapy

Start date of new anti-cancer drug therapy is used to determine the end of the on-treatment period (see Section [5.2.7](#)).

The start date of new anti-cancer drug therapy is the earliest start date of anti-cancer drug therapy recorded in the 'Follow-up Cancer Therapy' eCRF pages that is after the first dose of study treatment. When start date of anti-cancer drug therapy is missing or partially missing, the imputation rules described in Section [5.3.3.4](#) should be applied using only data from the 'Follow-up Cancer Therapy' eCRF pages.

5.2.6. Definition of start of new anti-cancer therapy

Start date of new anti-cancer therapy (drug, radiation, surgery) is used for censoring in efficacy analyses.

The start date of new anti-cancer therapy is the earliest date after the first dose of study treatment amongst the following:

- Start date of anti-cancer drug therapy recorded in the 'Follow-up Cancer Therapy' eCRF pages
- Start date of radiation therapy recorded in 'Radiation' eCRF page with 'Treatment Setting' = 'Curative'
- Surgery date recorded in 'Cancer Surgery' eCRF page when 'Surgery Outcome' = 'Resected' or 'Partially Resected'.

When start date of anti-cancer therapy is missing or partially missing, the imputation rules described in Section 5.3.3.4 should be applied using 'Follow-up Cancer Therapy', 'Radiation', and 'Cancer Surgery' eCRF pages.

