#### **6.9.8. Radiotherapy**

After the baseline PET/CT scan, radiotherapy is to be discussed with the Sponsor prior to initiation.

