### **Progression Free Survival**

PFS is defined as the time from the date of first dose until PD per Lugano Response Classification Criteria 2014, or death due to any cause, whichever occurs first.

PFS will be censored as follows:

- For participants who do not have an event (PD per Lugano Response Classification Criteria 2014 or death due to any cause), censoring will occur on the date of the last adequate disease assessment;
- For participants who start a new anticancer therapy prior to an event, censoring will occur on the date of the last adequate disease assessment before the new anticancer therapy;
- For participants with an event after a gap of 2 or more missing disease assessments, censoring will occur on the date of the last adequate disease assessment before the gap;
- Participants who do not have an adequate post-baseline disease assessment will be censored on the date of first dose of study intervention unless death occurs on or before the time of the second planned disease assessment (ie,  $\leq 24$  weeks after the date of first dose) in which case the death will be considered an event.

PFS will be summarized using Kaplan Meier method and displayed graphically. Median PFS and 2-sided 95% CI will be provided.

PFS will be summarized by dose levels for Phase 1b and Phase 2 of the study separately.

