OR is defined as a best overall response (BOR) of complete response (CR) or partial response (PR) according to Lugano Response Classification Criteria 2014. BOR will be assessed programmatically based on reported overall responses from the 'start date' until the first documentation of progressive disease (PD), death or start of new anti-cancer therapy, whichever occurs first.

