6.1.2.1. Main Analysis

- Estimand strategy: All OR data from Phase 2 will be included in the analysis.
- Analysis set: Safety Analysis Set.
- Intercurrent events and missing data: All data collected after an intercurrent event of subsequent anticancer therapy will be excluded. Participants who do not have a post-baseline disease assessment due to early PD, who receive anticancer therapies other than the study treatment prior to achieving an objective response, or who die, experience PD, or stop disease assessments for any reason prior to achieving an objective response will be counted as non-responders. Missing data will be imputed following Section 5.3.
- Analysis methodology: Assessment of response will be made as per investigator using Lugano 2014 response criteria. The analyses will be by treatment group.

Best overall response (BOR) will be assessed based on reported overall responses at different evaluation time points from the 'start date' until documented disease progression, according to the following rules. Only tumor assessments performed before the start of any further anti-cancer therapies will be considered in the assessment of BOR.

CR = at least 1 determination of CR before first documentation of progression

PR = at least 1 determination of PR before first documentation of progression (and not qualifying for a CR)

SD = at least 1 SD assessment \geq 6 weeks after the 'start date' and before first documentation of progression (and not qualifying for CR or PR).

PD = at least 1 PD assessment (and not qualifying for CR, PR or SD).

Not Evaluable (NE): all other cases.

Objective response (OR) is defined as BOR of CR or PR according to Lugano 2014 response criteria.

Patients who do not have an on-treatment tumor assessment due to early progression, who receive anti-tumor therapies other than the study treatments prior to reaching a CR or PR, or who die, progress, or drop out for any reason prior to reaching a CR or PR will be counted as non-responders in the assessment of OR. Each patient will have an objective response status (0: no OR; 1: OR). OR rate (ORR) is the proportion of patients with OR in the analysis set.

ORR by treatment group will be calculated along with the 2-sided 95% CI using the Wilson method (with continuity correction).

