6.6.1.4. Prior Anti-cancer Therapies

The prior anti-cancer therapies are collected under the 'Prior Cancer Therapy', 'Radiation' and 'Cancer Surgery' eCRF pages.

The number and percentage of patients in each of the following anti-cancer therapy categories will be tabulated:

- Patients with at least one type of prior anti-cancer therapy
- Patients with at least one prior anti-cancer drug therapy
- Patients with at least one prior anti-cancer radiotherapy (curative/palliative)

- Patients with at least one prior anti-cancer surgery
- Patients with at least one prior transplant
- Patients with prior CAR-T

Prior anti-cancer drug therapy will be summarized as follows based on the number and percentage of patients with the following:

- At least one prior anti-cancer drug therapy
- Number of prior anti-cancer drug therapy regimens: missing / 1 / 2 / 3 / 4 / ≥ 5

The prior anti-cancer drug therapies will also be summarized based on the number and percentage of patients by the drug class and preferred term. A patient will be counted only once within a given drug class and within a given drug name, even if he/she received the same medication at different times. The summary will be sorted on decreasing frequency of drug class and decreasing frequency of drug name in a given drug class. In case of equal frequency regarding drug class (respectively drug name), alphabetical order will be used.

Prior anti-cancer therapies will be included in the listings that follow with a flag to identify prior therapies. These will include the patient identification number, and all the relevant collected data-fields on the corresponding eCRF pages.

- Listing of anti-cancer drug therapies
- Listing of anti-cancer radiotherapy (curative/palliative)
- Listing of transplant
- Listing of anti-cancer surgeries

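### Palliative radiotherapy does not close the best-response window, so Phase 1b ORR and CR rate can count a response that follows radiation

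*SAP*

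**What the plan says.** SAP 5.2.6 defines the start of new anti-cancer therapy for efficacy and opens broadly: "Start date of new anti-cancer therapy (drug, radiation, surgery) is used for censoring in efficacy analyses". The list that follows narrows the radiation item to one setting: "Start date of radiation therapy recorded in 'Radiation' eCRF page with 'Treatment Setting' = 'Curative". The surgery item carries no such limit on intent: "Surgery date recorded in 'Cancer Surgery' eCRF page when 'Surgery Outcome' = 'Resected' or 'Partially Resected".

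Other parts of the plan draw no line between curative and palliative treatment:

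- SAP 3.1 describes the BOR window: "BOR will be assessed programmatically based on reported overall responses from the 'start date' until the first documentation of progressive disease (PD), death". It adds the start of new anti-cancer therapy as a further end point.
- SAP 6.1.2.1 states: "Only tumor assessments performed before the start of any further anti-cancer therapies will be considered in the assessment of BOR". It also counts anyone given other anticancer therapy before responding as a non-responder. SAP 6.2 applies a similar analysis to Phase 1b.
- SAP 6.6.1.4 has the category "Patients with at least one prior anti-cancer radiotherapy (curative/palliative").
- SAP 6.6.5 tabulates post-discontinuation anti-cancer therapy using the Radiation page, with no filter on setting.
- SAP 5.3.3.4 imputes missing start dates for radiation, again with no setting.

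On conduct, Protocol 6.9.2 bars additional anticancer therapy on study intervention before documented progression. Protocol 6.9.8 says: "After the baseline PET/CT scan, radiotherapy is to be discussed with the Sponsor prior to initiation".

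**The concern.** BOR is derived by program, so the result depends on which date the program takes as the end of the window. SAP 3.1 ends the window at the term that SAP 5.2.6 defines, and SAP 5.2.6 is the only operational definition for efficacy. A program built on it would ignore palliative radiation. A CR or PR seen after that radiation would count, although SAP 6.1.2.1 in plain words would exclude it.

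At stake is attribution. ORR and CR rate are the main activity summaries still to be reported, and they are meant to describe the combination. If radiation shrank the lesion, the rate describes something else.

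**Working it through.** **1. Does another rule catch the case?** The definitions of adequate baseline and post-baseline assessment (SAP 5.2.10 and 5.2.11), Protocol 8.2 and Protocol Appendix 12 were checked. None makes an irradiated lesion non-evaluable. Protocol 8.2 also continues scans after study intervention stops before progression, whatever other treatment intervenes. The bar in Protocol 6.9.2 no longer applies at that point.

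**2. Can one irradiated site decide the response?** Yes. Protocol 5.1 requires only one measurable, PET-avid site. With several sites, irradiating one need not produce a CR or PR, because Appendix 12 judges the PET-CT score or the sum over up to six target sites.

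**3. Direction.** SAP 6.1.2.1 needs only one CR or PR determination before progression. A longer window can add qualifying assessments but cannot remove any. So, for each participant, OR and CR status under the present rule is the same as or better than under a window closed at radiation. The difference in ORR and CR rate therefore cannot be negative. For OR, the relevant radiation falls before the first response. For CR it may also fall between a PR and a CR.

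**4. The plan's own figure.** SAP Table 2 gives Wilson intervals with continuity correction at n = 25. With q = 1 − p and z = 1.96:

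- lower = [2np + z² − 1 − z√(z² − 2 − 1/n + 4p(nq + 1))] / [2(n + z²)]
- upper = [2np + z² + 1 + z√(z² + 2 − 1/n + 4p(nq − 1))] / [2(n + z²)]

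For 15/25 these give 0.389 and 0.782, as tabulated. All 19 rows reproduce to three decimals, and the table is not in dispute.

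**5. Size of one case.** The shift in ORR is 1/n. Protocol 9.6 gives about 20 participants in Phase 1b and about 6 to 9 DLT-evaluable participants at the MTD or highest safe tested dose. Starting response counts are illustrative.

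| n | With the case (95% CI) | Without it (95% CI) | Shift |
|---|---|---|---|
| 6 | 4/6 = 0.667 (0.241, 0.940) | 3/6 = 0.500 (0.139, 0.861) | 1/6 = 16.7 points |
| 9 | 5/9 = 0.556 (0.227, 0.847) | 4/9 = 0.444 (0.153, 0.773) | 1/9 = 11.1 points |
| 20 | 12/20 = 0.600 (0.364, 0.800) | 11/20 = 0.550 (0.320, 0.762) | 1/20 = 5 points |

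SAP 5.2 reports by dose level, so the first two rows are closer to what will be shown. The row for 20 is a pooled figure. Efficacy uses the Safety Analysis Set, so actual denominators may differ from 6 and 9.

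**The case against.** The strongest reply is that the event should be rare and its consequence small. Protocol 6.9.2 restricts additional anticancer therapy, and 6.9.8 requires discussion without granting permission. A reader might infer that the protocol allows palliative radiation, or that on-study radiation will mostly be palliative. The documents support neither. This limits frequency, but these are conduct rules and do not say how a case is analysed.

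A reader might also infer that DoR and PFS are biased upward. That is not shown. Under the present rule follow-up continues after palliative radiation, and a later progression or death still counts. The protocol's PFS rule, "For participants who start a new anticancer therapy prior to an event", censors at the last adequate assessment before the new therapy. Extending it to palliative radiation would censor people who may be irradiated because they are worsening. Such censoring can be informative and may itself raise the Kaplan-Meier curve. This objection stands, and the point is confined to OR and CR.

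Nor does the statement in SAP 2.1 that there are no modifications clearly fail. The protocol never defines which radiotherapy counts and leaves detail to the SAP.

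Finally, the Imaging Manual and the cited guidance on applying the Lugano criteria are not available here. Either may contain a rule for irradiated lesions. The SAP does not invoke one when deriving BOR.

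**Conclusion.** The concern holds for ORR and CR rate. The only operational definition omits palliative radiotherapy, while the BOR rule and the SAP's own vocabulary include it. No visible rule stops a CR or PR after palliative radiation from counting.

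Protocol section 9 states that Phase 2 will not start and its endpoints will not be analysed. What remains is descriptive secondary efficacy in Phase 1b; the primary DLT endpoint is untouched. Each case is worth 17 points at n = 6, 11 points at n = 9 and 5 points at n = 20.

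These figures assume that at least one such case occurs and that its response would not have been counted under a closed window. The number of cases is unknown and may be zero. Radiation after documented progression is irrelevant, because progression has already closed the window.

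**What to change.** In SAP 5.2.6 and 6.1.2.1, add a rule for BOR, OR and CR. The assessment window closes at the start of any radiation after first dose to a lymphoma site used in the response assessment (target, measured or FDG-avid), whatever its recorded setting. FDG-avid sites belong in the rule because a PET-based CR is not confined to measured lesions. List every affected participant with radiation date, site and later assessments.

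Leave the main censoring rule for DoR, DoCR and PFS as it is. At most, add a sensitivity analysis that censors at palliative radiation. Participants who cease to be responders drop out of DoR, and those who cease to be complete responders drop out of DoCR.

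The cost is a short SAP edit using a page the trial already collects, plus the radiation site. The documents do not show whether that page records the site. ORR and CR rate may be slightly lower, and a genuine drug response first seen after radiation would be lost. SAP Version 2 is based on Protocol Amendment 1, so the edit could go into a revision aligned with Amendment 2.
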